7.3 Adverse Events and Serious Adverse Events

Adverse events (AEs) and serious adverse events (SAEs) are defined as follows.

An **adverse event (AE)** is defined as any unfavorable and unintended diagnosis, symptom, sign (including an abnormal laboratory finding), syndrome or disease which either occurs during the study, having been absent at baseline, or if present at baseline, appears to worsen.

A serious adverse event (SAE) is defined as any untoward medical occurrence that results in death, is life threatening, requires inpatient hospitalization or prolongation of existing hospitalization, results in persistent or significant disability/incapacity, or is a congenital anomaly.

These events will be assessed at each visit using the adverse events monitoring form and rated as mild, moderate, or severe. These parameters are defined as follows: mild (noted change in the subject's condition that causes minor distress and does not affect activity); moderate (notable distress and or mild disruption in usual activity); and severe (marked distress and/or major disruption in usual activity).

7.4 Reporting Procedures

Unexpected, serious, and intervention-related SAEs will be reported to the NYU, BU and MGH IRBs, DSMB, and NCCAM, in accordance with requirements. Unexpected fatal or lifethreatening AEs related to the intervention will be reported to the NCCAM Program Officer within 7 days. Other serious and unexpected AEs related to the intervention will be reported to the NCCAM Program Officer within 15 days. Anticipated or unrelated SAEs will be handled in a less urgent manner but will be reported to the DSMB, IRB, NCCAM, and other oversight organizations in accordance with their requirements.

7.5 Follow-up for Adverse Events

We will first administer the SAFTEY form at each visit. This form asks if any AE's have occurred. If the subject answers "yes" we will then fill out the cumulative AE LOG accordingly.

Adverse events will be assessed at each visit using the adverse events monitoring form and rated as mild, moderate, or severe. These parameters are defined as follows: mild (noted change in the subject's condition that causes minor distress and does not affect activity); moderate (notable distress and or mild disruption in usual activity); and severe (marked distress and/or major disruption in usual activity).

7.6 Safety Monitoring

This study will be overseen by a study DSMB and associated DSMP, as well as the IRB at each study site. Additional monitoring by NCCAM may occur.

2. Frequency of Data Review for this Study— The frequency of data review for this study differs according to the type of data and can be summarized in the following table:

Data type	Frequency of review	Reviewer		
Summary figure of subject accrual & summary table of reasons for exclusion (based on protocol enrollment criteria)	PIs weekly for first three months of recruitment, then weekly accrual and quarterly adherence; DSMB yearly	PI, DSMB		
Summary table of status of all randomized subjects, as of date of reporting	PIs monthly, DSMB yearly	PI, DSMB		
Summary tables of adherence to IE visits and treatment sessions	PIs quarterly, DSMB yearly	PI, DSMB		
Summary table of demographic characteristics of all randomized subjects	PIs monthly, DSMB yearly	PI, DSMB		
Summary tables of all (serious) adverse events	PIs quarterly, DSMB yearly	PI, DSMB		
Detailed descriptions of SAEs	Per Occurrence	PI, DSMB, IRB, NCCAM		
Full study continuing review	Yearly	IRB (MGH, BU, and NYU respectively)		

8. INTERVENTION DISCONTINUATION

8.1 Treatment Discontinuation and Monitoring:

Any participant with a CGI-I of 5 or greater at any time will undergo weekly assessment by a study clinician including clinical and safety assessments, CGI-S and CGI-I ratings and suicidality assessment (CSS suicidality checklist) Participants will be discontinued from study participation at their request at any time or if warranted in the clinical judgment of the study clinicians. Additionally, participants who score >5 on the Clinical Global Impression of Improvement Scale for 2 consecutive weeks (much worse) or who develop suicidality at any point will be discontinued from the treatment protocol and referred for clinically appropriate care. In these instances, the subject will be evaluated by a study clinician and a decision will be made regarding possible exit from the study and/or referral for treatment. We will report all episodes of worsening symptoms and the outcome of the attendant monitoring procedure to our DSMB.

In addition, if the BDI-II suicidality item (item number nine) is above 1 (scale is from 0 to 3) or the CSS suicide checklist is above 2, a study clinician will assess the patient weekly to determine suicidality and if present, assist with accessing any indicated clinical intervention. This assessment will occur weekly until the BDI-II item is no longer above a 1 and CSS suicidality item is no longer above 2.

Twenty-four-hour emergency coverage with a study clinician (physician, psychologist, or registered nurse with MD oversight) will be available. Patients will be provided with cards with the emergency contact number. In the event of an emergency the clinician will determine the necessary clinical intervention and will provide and coordinate appropriate care.

All participants will be encouraged to complete a final endpoint assessment unless clinically inappropriate even if they discontinue treatment, and all analyses will be intent to treat. Every effort will be made to keep appropriate subjects in the study for the full duration of the trial. Subjects dropping out of the trial will be included in data analysis as described in the Data Analysis Section.

Non responders (CGI-I >2) will be assisted in finding appropriate care from our existing referral resources. Additional treatments will be monitored and considered in the analyses. Furthermore, subjects who wish to discontinue their participation at any point will also receive referral assistance if they request additional treatment.

If at any time during the course of the study, the DSMB judges that risk to subjects outweighs the potential benefits, the DSMB shall have the discretion and responsibility to recommend that the study be terminated.

9. STATISTICAL CONSIDERATIONS

9.1 General Design Issues

The specific aims and hypotheses are as follows:

Specific Aim 1: Short-term Efficacy of Yoga: Our primary objective is to examine the short-term treatment efficacy of yoga on GAD symptoms. We expect that, at post-treatment, a significantly greater proportion of individuals randomized to receive yoga will be classified as "responders" to treatment (CGI-I ≤ 2) than for individuals who receive SE (Hypothesis 1.1). We further expect

that a greater proportion of individuals receiving CBT for GAD will be classified as "responders" than for those receiving SE (Hypothesis 1.2). Moreover, we predict that the rate of "responders" in individuals receiving yoga will be comparable to those receiving CBT at post-treatment (Hypothesis 1.3).

Specific Aim 2: Long-term Efficacy of Yoga (Exploratory Aim): Our secondary aim is to examine the long-term treatment efficacy of yoga on GAD symptoms. We hypothesize that yoga and CBT will be equally effective at the 6-month follow-up (i.e., the "responder" rate for yoga will not be inferior to that for CBT), and that yoga and CBT will each have higher "responder" rates than SE (Hypothesis 2.1-2.3).

Specific Aim 3: Mediation Analyses. Our tertiary aim is to examine and compare the mechanism of treatment changes in yoga and traditional CBT for GAD. We predict that treatment changes in responder rates during yoga treatment will be mediated via changes in mindfulness and changes in vagal tone (Hypothesis 3.1), whereas changes in CBT will be mediated via changes in maladaptive cognitions (Hypothesis 3.2.). Moderators of "responder rates" will also be examined.

These hypotheses can be tested in a five-year multi-site study to examine the comparative efficacy of yoga, CBT, and stress education, a previously employed control condition, for patients with GAD. Patients with GAD will receive 12-weekly yoga, CBT, or stress education sessions delivered in a group format controlling for attention, time, and group format. Independent evaluators will perform assessments before the 12-session intervention phase, at mid-treatment, after the intervention, and at 6-month follow-up.

9.2 Sample Size and Randomization

A non-inferiority test is the most direct test of our hypothesis that Yoga will be as effective as CBT for both short-term and long-term outcomes. We will perform a non-inferiority test using response rate (response rate is defined as CGI-I ≤ 2) as the outcome on which to compare CBT and Yoga at posttreatment and at follow-up. Since some attrition may occur, we will use last observation carried forward to insure an intent-to-treat analysis. The non-inferiority margin will be half the difference in response rates between the active comparison (CBT) and placebo. Based on earlier literature, we can expect response rates in our particular CBT and placebo conditions of 57.9% in CBT and 22.2% in placebo. Thus, our non-inferiority margin will be set at ¹/₂ the difference between 56.7 and 22.2, or 17.85%. Using the power analysis program PASS 12, we find that the number of subjects required to obtain .80 power for the non-inferiority test comparing CBT and Yoga is 95 participants in each of the 2 conditions. We verified this number in a 1000 simulation Monte Carlo study using these same parameters. This number is higher than the number proposed in the original grant. Thus, we will increase the N per cell in CBT and Yoga to 95 (22 additional patients per site) to have adequate power for this non-inferiority test. While the original study was budgeted based on a lower number of participants, with careful management of costs we believe we can manage this increase in participants within the full study budget if awarded as proposed.

For the superiority tests (CBT vs. SE and Yoga vs. SE) on the secondary outcomes (which are continuous), we used the MRM power analysis program PinT 2.12. We assumed 25% missing data, and used data from our recent CBT trials (e.g., Stern et al., 2012) to estimate the variances and covariances needed for PinT. PinT indicated greater than .80 power to detect an effect size as small as d=.27, between a small (d=.20) and medium (d=.50) effect size.

We predict that changes in mindfulness will mediate changes in outcome over time for patients in the Yoga condition, and changes in cognitions will mediate changes in CBT. Plus, changes in RSA and cortisol may also mediate changes in outcome across conditions. We further predict that treatment condition will moderate the effect of Time on the mediators ("a" paths).

We performed a Monte Carlo study to calculate the power for our proposed bootstrap mediation analysis. Based on our recent trial, we assumed that the "a" paths (the effects Yoga vs. SE and of CBT vs. SE on the mediators) would be large, and that the relation between each mediator and the outcome (response to treatment) would have a medium effect size. The Monte Carlo study consisted of 400 samples, for each of which we performed a bootstrap mediation analysis, each consisting of 1,000 resamples for the bootstrap analysis. Results showed a power greater than .81 to detect a mediated pathway.

Treatment Assignment Procedures

Please see Randomization procedures section 4.3.

Independent evaluators will remain blind to treatment assignment throughout the study. To preserve the blind they will be instructed with a reminder script for patients not to discuss their treatment prior to an assessment. The randomization codes will be created by the study statistician prior to entry of the first patient in the trial. Randomization will be stratified only by site. No unblinded analyses will be performed prior to study completion, unless specifically requested by the DSMB, in which case study PIs will only see blinded safety comparisons of the study intervention groups.

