9.5 Outcomes

As noted earlier, a non-inferiority test is the most direct test of our hypothesis that Yoga will be as effective as CBT for both short-term and long-term outcomes. We will perform a non-inferiority test using response rate (response rate is defined as CGI-I \leq 2) as the outcome on which to compare CBT and Yoga at post-treatment and at follow-up. Since some attrition may occur, we will use last observation carried forward to insure an intent-to-treat analysis. The non-inferiority margin will be half the difference in response rates between the active comparison (CBT) and placebo. Based on earlier literature, we can expect response rates in our particular CBT and placebo conditions of 57.9% in CBT and 22.2% in placebo. Thus, our non-inferiority margin will be set at 1/2 the difference between 56.7 and 22.2, or 17.85%. Using the power analysis program PASS 12, we find that the number of subjects required to obtain .80 power for the non-inferiority test comparing CBT and Yoga is 95 participants in each of the 2 conditions. We verified this number in a 1000 simulation Monte Carlo study using these same parameters. This number is higher than the number proposed in the original grant. Thus, we will increase the N per cell in CBT and Yoga to 95 (22 additional patients per site) to have adequate power for this non-inferiority test. While the original study was budgeted based on a lower number of participants, with careful management of costs we believe we can manage this increase in participants within the full study budget if awarded as proposed.

For the superiority tests (CBT vs. SE and Yoga vs. SE) on the secondary outcomes (which are continuous), we used the MRM power analysis program PinT 2.12. We assumed 25% missing data, and used data from our recent CBT trials (e.g., Stern et al., 2012) to estimate the variances and covariances needed for PinT. PinT indicated greater than .80 power to detect an effect size as small as d=.27, between a small (d=.20) and medium (d=.50) effect size.

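### The claim that yoga is non-inferior to CBT is not made conditional on CBT beating stress education in this trial, although the 17.85-point margin presupposes that CBT works

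*Combined protocol and SAP*

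**What the plan says.** Section 9.1 lists three Aim 1 hypotheses side by side. Hypothesis 1.1 is that more patients respond on yoga than on SE. Hypothesis 1.2 is the same for CBT, a higher proportion of responders "than for those receiving SE (Hypothesis 1.2"). Hypothesis 1.3 is that "the rate of 'responders' in individuals receiving yoga will be comparable to those receiving CBT at post-treatment (Hypothesis 1.3"). Section 1.1 repeats them.

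Sections 9.2 and 9.5 turn Hypothesis 1.3 into a non-inferiority test; 9.5 says "a non-inferiority test is the most direct test of our hypothesis that Yoga will be as effective as CBT". The margin rule is "The non-inferiority margin will be half the difference in response rates between the active comparison (CBT) and placebo". Its inputs come from earlier literature: "response rates in our particular CBT and placebo conditions of 57.9% in CBT and 22.2% in placebo". The result is a fixed number: half of "the difference between 56.7 and 22.2, or 17.85"%.

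Section 3 assigns a superiority test to yoga vs SE and a non-inferiority test to yoga vs CBT, and does not link them. Section 9.6 reads yoga vs SE and CBT vs SE from two separate model coefficients. Sections 9.1 to 9.6 contain no testing order and no statement that the yoga-CBT conclusion depends on CBT vs SE. No alpha is given for any of the three tests.

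**The concern.** A margin equal to half of CBT's effect has its intended meaning only if CBT has roughly that effect here. The assumed effect is 57.9 − 22.2 = 35.7 points. If the true CBT-SE difference is much smaller, 17.85 points can be as large as the whole effect. Being within 17.85 points of CBT then says nothing about whether yoga helps.

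The documents give reason to take this seriously. The 22.2% is a literature placebo rate. SE is described in 2.2 and 5.1 as an active control for attention, expectancy and group support. It matches the other arms in session length and format, includes home practice and comes with a credible rationale. A response rate above 22.2% would not be surprising. At an SE rate of 40%, a CBT rate of 57.9% leaves an effect of 17.9 points, almost exactly the margin.

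The design already contains the arm and the test that would detect this. Only the decision rule connecting them is missing.

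**Working it through.** **Inputs from the documents.** Yoga 95, CBT 95, SE 40 (Précis); CBT 57.9%, placebo 22.2%, margin 17.85 points, power .80 (9.2).

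**Assumptions.** Non-inferiority: Wald test at one-sided 0.05, also shown at 0.025. CBT vs SE: pooled z test at two-sided 0.05. Patients are independent and there is no dropout. The documents state no alpha and give no intraclass correlation.

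**1. The margin.** (57.9 − 22.2)/2 = 17.85. The 56.7 printed in the same sentence would give 17.25; that is a separate discrepancy, and 57.9 and 17.85 are used here.

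**2. The plan's sample size.** The plan says "the number of subjects required to obtain .80 power for the non-inferiority test comparing CBT and Yoga is 95 participants" per arm. With n = 2p(1−p)(z₁₋α + z₀.₈₀)²/margin²:
- one-sided 0.05: 2 × .579 × .421 × (1.645 + 0.842)²/.1785² = 94.6, so 95. This reproduces the plan.
- one-sided 0.025: 120.1, so 121. This does not.

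The plan's figure therefore implies one-sided 0.05.

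**3. Probability of declaring non-inferiority when all arms respond at the same rate p.** It is approximately Φ(.1785/s − z₁₋α), with s = √(2p(1−p)/95).
- p = .222: s = .0603; Φ(2.960 − 1.645) = Φ(1.315) = .906.
- p = .40: s = .0711; Φ(2.512 − 1.645) = Φ(0.867) = .807.

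**4. Power of CBT vs SE at the planning rates.** The pooled rate is (95 × .579 + 40 × .222)/135 = .473. The pooled SE is .0941 and the unpooled SE is .0830. Power = Φ((.357 − 1.96 × .0941)/.0830) = Φ(2.08) = .981.

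**5. Joint probabilities.** Both tests use the same CBT arm, so their probabilities cannot simply be multiplied. A run of 400,000 simulated trials and an exact binomial enumeration agree to within simulation error. Results at one-sided 0.05 for non-inferiority (NI):

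| True rates CBT / yoga / SE | NI declared | CBT beats SE | Both |
|---|---|---|---|
| 22.2 / 22.2 / 22.2 | .907 | .023 | .015 |
| 40 / 40 / 40 | .802 | .024 | .011 |
| 57.9 / 57.9 / 22.2 (planning) | .794 | .979 | .774 |
| 57.9 / 57.9 / 35 | .794 | .69 | .51 |
| 57.9 / 57.9 / 40 | .794 | .48 | .34 |
| 40 / 40 / 22.2 | .80 | .52 | .37 |

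The first two rows show what the condition prevents. The last four show what it costs when CBT truly beats SE and yoga truly equals CBT.

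**6. At one-sided 0.025 for NI.** The equal-arm figures are 84% (22.2%) and 71% (40%). Planning power is about .70, or .68 with the condition. The finding does not hinge on the alpha assumption.

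**The case against.** Five objections deserve an answer.

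- **The 91% and 80% might be read as false-positive rates for non-inferiority. They are not.** With equal arms, yoga really is no worse than CBT. What fails is the further inference that yoga works, and Hypothesis 1.1 tests that directly: with all arms at 22.2%, yoga beats SE in only about 2% of trials. This stands. It limits the harm to the reading of the comparative claim.
- **A reader might infer that the plan licenses a non-inferiority claim whatever CBT does against SE.** It contains no such statement. The Précis predicts jointly that yoga and CBT each beat SE and do not differ from each other. The gap is an unstated condition. Still, a prediction is not a decision rule, and reporting CBT vs SE alongside does not withhold the claim.
- **One might go further and ask for a full fixed sequence, with CBT vs SE ahead of yoga vs SE.** The documents do not support that. Yoga's short-term efficacy is the primary objective and Hypothesis 1.1 its first hypothesis. With yoga at 57.9%, CBT at 40% and SE at 22.2%, such a sequence would cut the power for yoga vs SE from .98 to .52. The validity of the margin gives no reason for it.
- **The event is rare if the plan's assumptions hold.** At the planning rates, non-inferiority without CBT beating SE occurs in about 2% of trials. Section 2.2 also cites a CBT effect in GAD of g = 0.51 (95% CI 0.05 to 0.97), so a null CBT effect is not the expected case. This is fair; the condition is insurance against those rates failing.
- **The condition can block correct claims**, as the last three rows of the table show. That also stands and belongs in the stated cost.

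**Conclusion.** The point holds as an omission in the decision rule. The margin is fixed from outside data, its meaning depends on CBT working here, and the plan does not tie Hypothesis 1.3 to Hypothesis 1.2. If CBT has no effect and the arms are equal, the plan as written yields a non-inferiority declaration in about 80% to 91% of trials (71% to 84% at one-sided 0.025). With the condition, the rate is about 1% to 1.5%.

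These figures rest on the assumed alphas, simple two-sample tests, independent patients and complete data. The plan's group-based delivery and the expected 20% discontinuation are not modelled. The finding does not mean that the trial's answer on yoga vs SE is unreliable, or that Hypothesis 1.1 needs to wait on anything.

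**What to change.** Add to 9.6: *Non-inferiority of yoga to CBT at post-treatment (Hypothesis 1.3) will be claimed only if CBT is significantly superior to SE at post-treatment in this trial (Hypothesis 1.2); otherwise the yoga-CBT comparison will be reported as inconclusive.* Name the significance level of both tests, since the sentence cannot be applied without them. Leave Hypothesis 1.1 unconditional. Keep the follow-up comparisons exploratory, as 9.1 and 9.6 already state.

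The change needs no extra patients, visits or data. At the planning rates it costs about 2 points of non-inferiority power (.794 to .774). Because SE has only 40 patients, the cost rises quickly away from those rates: .79 to .51 with SE at 35%, .79 to .34 with SE at 40%, and .80 to .37 with CBT and yoga at 40% and SE at 22.2%. The plan should state these figures beside the rule. Label: cheap improvement.

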3. STUDY DESIGN

The purpose of the proposed study is to determine whether yoga is an effective method for treating GAD, and its relative efficacy compared to a standard psychosocial intervention. For this purpose, we will conduct a randomized controlled trial. Using superiority tests, yoga (N = 95) will be compared to SE (N = 40), a commonly used control condition. Using non-inferiority tests, yoga will compared to standard CBT for GAD (N = 95). To improve comparisons, all interventions will be conducted in a group format over 12 weekly sessions with 4-6 patients per group and therapists/yoga instructors. We anticipate having approximately 3 yoga instructors, 3 CBT therapists, and 3 SE instructors, along with 2 IEs per enrolling site. All interventions will be conducted at anxiety out-patient clinics in Boston (the Center for Anxiety and Related Disorders at Boston University and the Center for Anxiety and Traumatic Stress Disorders at Massachusetts General Hospital). The third study site, NYU Langone Medical Center in New York City, will not recruit participants and will conduct data analysis and interpretation as well as study oversight. Subjects in all 3 treatment groups will be provided with a credible rationale for the efficacy of their assigned treatment. At each study treatment visit, patients will complete various psychological measures. Some of the study visits require more in-depth assessments involving saliva sample collection, meeting with a study doctor, and a physical examination (see the section 6.1 for more information). The four independent evaluator blinded assessments occur pre-treatment (baseline visit), mid-treatment (Week 6), post-treatment (Week 12), and at a sixmonth follow-up.

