Our study statisticians will set up the randomization table stratified by site and with variablesized permuted blocks (maximum block size will be 6 to minimize cohort effects). The variablesized permuted block randomization schedules will be generated by [name] (the supervising biostatistician) prior to enrolling the first subject into the study. Randomization will be stratified by site, and groups of 4-6 individuals will be randomized at a time to one of the 3 treatment conditions. Randomizations will be conducted in SAS using the procedures outlined by Efird (2011) [Efird, J. Blocked Randomization with Randomly Selected Block Sizes. *Int. J. Environ. Res. Public Health.*, *8*, *15-20.J.* The randomization code will be emailed by [name] (the trial statistician) to the study coordinator only when the randomization occurs, i.e. once the last participant of each group has completed baseline.

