9.6 Data Analyses

Primary Analyses

Our primary analyses will use mixed-effects regression models (MRMs) with a logistic linking function (a GLMM analysis) since our primary outcome measure (response to treatment, defined as CGI-I≤2) is dichotomous. Analyses of secondary outcomes will be performed using MRM. MRM and GLMM easily accommodate nesting of repeated observations within subjects, include all subjects with at least one assessment, and are the preferred method to analyze longitudinal data (Hamer and Simpson, 2009 [135]). Since these analyses will include all subjects who are randomized and complete at least one assessment, it is an intent-to-treat analysis. Also, since subjects will undergo treatment in groups (4-6 subjects per group) our MRM and GLMM models will include 3 levels: repeated measurements (level 1) nested within subjects (level 2) who will be nested within their treatment cohort (level 3).

Our primary model will be a GLMM in which response to treatment over time will be modeled as a growth curve. Our primary analyses will examine outcomes at post-treatment (Aim 1). These analyses will include only the 7 assessments from baseline to post-treatment, and will not include the follow-up (FU) assessment since it could be affected by subjects seeking other treatments during the FU period. Only our exploratory analyses for outcome at FU (Aim 2) will include data from the FU assessment. Since recent research indicates that suboptimal modeling of the growth curve can result in incorrect results, we will examine various linear and nonlinear models to find the optimal growth curve during treatment (linear, quadratic, cubic, exponential [leveling off at an asymptote], and an ANOVA model, in which time is coded as a categorical variable. For this ANOVA model, each assessment time point is modeled with a dummy coded assessment variable [coded 1 for the assessment, 0 for other assessments]. In this model, the means at each assessment point are freely estimated and are not constrained to fit any particular pattern. See our discussion of the ANOVA model in the paragraph below for more information).We will conduct our significance tests using the growth curve that most accurately models the data (comparing the various growth curve models using AIC and BIC).

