The three treatment conditions (Yoga, CBT, and SE) will be coded using 2 dummy variable contrasts, with SE as the "reference" treatment. The first dummy variable will contrast Yoga vs. SE, and the second will contrast CBT to SE. Time will be coded as weeks since baseline. To test of differences between treatments at post-treatment (week 12), time will be centered at week 12 (in other words, our Time variable in our analysis will be computed as "time minus 12"). In MRM or GLMM analyses in which this Time centered variable is used, the significance of the dummy variable contrasts (Yoga vs. SE and CBT vs. SE) provides the test of the differences between treatment conditions at post-treatment. A similar approach can be used to test differences between treatment conditions at follow-up.

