To determine if the results of the analyses for Aim 1 are sensitive to the growth curve model, we will perform a secondary analysis, using a simple ANCOVA-type model, to verify the results of our primary growth curve model. Since the outcome is binary (response to treatment), this analysis will be performed using logistic regression, with the following predictors of outcome at post-treatment: baseline severity based on the CGI-S and SIGH-A, and the two dummy variables coding the contrast between SE and the 2 active treatments. This analysis will be performed twice: once as an ITT analysis with missing outcomes imputed as last observation carried forward, and once as a completer analysis.

Per Protocol Secondary Analysis:

As additional secondary analyses, we will repeat our GLMM and MRM analyses using the per protocol sample. We will use these analyses rather than simpler analyses (such as logistic regression or repeated measures ANOVA) because repeating our GLMM and MRMs will allow a more direct comparison to the results for the intent-to-treat sample, allows inclusion of subjects that miss some assessments (other than baseline and post-treatment), allows the modeling of complex covariances between the repeated measures, and it assumes MAR rather than MCAR.

Follow Up Secondary Analyses:

Analyses of outcome at FU (Aim 2) will be considered exploratory since subjects may seek additional treatment during follow-up. These analyses will follow the analyses of outcome at post-treatment, except one additional assessment (FU) will be added to these analyses. Since response during FU may not follow the growth curve of the treatment phase, the growth curve for Aim 2 will be modeled as "piecewise", separately modeling the growth curve during treatment and follow-up. (Analyses of the secondary outcomes at FU will follow the mixed effects ANOVA model described above since these analyses include only 4 total assessments). We will add an additional dummy variable predictor to the analyses for Aim 2, coding whether or not the subject received additional treatment during FU. We will also add the interactions of this "additional treatment" variable with all the other predictors in the analyses to determine if "additional treatment" impacted response to treatment at FU. This analysis will

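### The .80 power for the yoga–CBT non-inferiority test holds only if patients are independent, although treatment is given in groups of 4–6 and Section 9.6 models the cohort

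*Combined protocol and SAP*

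**What the plan says.** Sections 9.2 and 9.5 carry the same sizing text. The expected response rates are 57.9% for CBT and 22.2% for placebo, the margin is half the difference (17.85 points), and the conclusion is that the "number of subjects required to obtain .80 power for the non-inferiority test comparing CBT and Yoga is 95 participants" in each of the two arms. The authors add: "We verified this number in a 1000 simulation Monte Carlo study using these same parameters". For attrition in this test, "we will use last observation carried forward to insure an intent-to-treat analysis". No ICC, cohort size or design effect is listed, and neither is an alpha level or sidedness.

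Elsewhere the plan treats cohorts as a feature of the data. Section 3 says "all interventions will be conducted in a group format over 12 weekly sessions with 4-6 patients per group". Section 4.3 sets the block size with cohorts in mind ("maximum block size will be 6 to minimize cohort effects"). Section 9.6 says "since subjects will undergo treatment in groups (4-6 subjects per group) our MRM and GLMM models will include 3 levels", with treatment cohort as the third.

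The treatment coding in 9.6 is: "The first dummy variable will contrast Yoga vs. SE, and the second will contrast CBT to SE". Its logistic-regression sensitivity analysis is run "once as an ITT analysis with missing outcomes imputed as last observation carried forward" and again on completers. The predictors listed there are baseline CGI-S and SIGH-A severity and the two treatment dummies, with no cohort term.

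**The concern.** Patients treated in one group share an instructor, a timetable and each other, so their responses may be correlated. If they are, 95 patients per arm carry less information than 95 independent patients. The plan accepts this in its modelling section but not in its sizing.

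The gap matters because the yoga versus CBT comparison (Hypothesis 1.3) sets the size of both large arms. There are two possibilities:

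- If the test allows for cohorts, its power is below the stated .80.
- If it does not, less power is lost, but with enough correlation the standard error is too small and yoga is declared non-inferior to CBT too often.

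The plan does not say which applies. The non-inferiority test is described only as a response-rate comparison with last observation carried forward (LOCF). The three-level model uses available assessments, works on the logit scale and is coded only against SE.

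**Working it through.** **Inputs.** From 9.2: response 57.9% (CBT), margin 0.1785, 95 per arm, power .80. From Section 3: cohort size m = 4 to 6. Assumed: yoga response also 57.9%; one-sided alpha 0.05, chosen because it returns the printed 95; ICC from 0 to 0.10, because the documents give none for cohorts (their only ICC is a rater-reliability criterion).

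**Step 1: reproduce the printed figure, independent patients.**

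n = (1.645 + 0.842)² × 2 × 0.579 × 0.421 / 0.1785² = 94.6, so 95 per arm.

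SE at 95 per arm = √(2 × 0.579 × 0.421 / 95) = 0.0716. Power = Φ(0.1785/0.0716 − 1.645) = 0.801.

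At one-sided 0.025 the same formulas give power 0.703 at 95 and n = 120.1, before any clustering.

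**Step 2: cohort-aware test, normal approximation.** Multiply the variance by the design effect DE = 1 + (m − 1) × ICC. For m = 5 and ICC 0.05, DE = 1.20, the effective sample is 95/1.20 = 79 per arm, and power is 0.736.

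| ICC | m = 4 | m = 5 | m = 6 |
|---|---|---|---|
| 0 | 0.801 | 0.801 | 0.801 |
| 0.01 | 0.791 | 0.788 | 0.784 |
| 0.02 | 0.781 | 0.774 | 0.768 |
| 0.05 | 0.751 | 0.736 | 0.720 |
| 0.10 | 0.706 | 0.678 | 0.652 |

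On this formula power falls below .80 at an ICC of about 0.001 for m = 5.

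**Step 3: cohort-level t-test, simulated.** Beta-binomial responses, 100,000 runs, 95 per arm in 24, 19 or 16 cohorts (46, 36 or 30 degrees of freedom). The ICC 0 row shows what the t-test costs by itself.

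| ICC | m = 4 | m = 5 | m = 6 |
|---|---|---|---|
| 0 | 0.789 | 0.787 | 0.782 |
| 0.01 | 0.781 | 0.774 | 0.765 |
| 0.02 | 0.766 | 0.758 | 0.750 |
| 0.05 | 0.737 | 0.719 | 0.700 |
| 0.10 | 0.692 | 0.660 | 0.633 |

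Its type I error is 0.045–0.047 throughout.

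**Step 4: test that ignores cohorts.** Unpooled z-test. The ICC 0 row is exact enumeration; the other rows come from the same simulation. Ranges run over m = 4 to 6. Type I error is taken at the margin (yoga 40.05%, CBT 57.9%).

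| ICC | Power | One-sided type I error |
|---|---|---|
| 0 | 0.794 | 0.046 |
| 0.01 | 0.787–0.793 | 0.048–0.050 |
| 0.02 | 0.784–0.787 | 0.050–0.053 |
| 0.05 | 0.769–0.777 | 0.056–0.065 |
| 0.10 | 0.752–0.766 | 0.070–0.086 |

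**Step 5: can the plan's text settle which test applies?** The three-level model has a cohort term but neither LOCF nor a stated yoga–CBT contrast. The non-inferiority test has LOCF and a percentage-point margin but no stated standard error. The other LOCF analysis, the logistic regression, lists no cohort term. So the text does not settle it.

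**The case against.** **The printed 95 is not a miscalculation.** This is true. It reproduces, and the fault is an unstated independence assumption and an unspecified variance.

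**Small losses are within the noise of the choice of test.** This is partly right. With independent patients the exact power of the unpooled test is already 0.794, and a score test gives 0.808 at 95 per arm. The cohort-level t-test loses 1–2 points from its degrees of freedom alone. The losses in Steps 3 and 4 should therefore be read against their own ICC 0 rows, not against .80. At ICC 0.01–0.02 the effect of clustering is small and type I error is essentially nominal.

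**Material harm needs an ICC of about 0.05 or more, and nothing in the documents supports one.** Nothing in them rules it out either. The range is shown for that reason, and only the omission, not the size of the loss, is certain.

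**The three-level model already covers Aim 1, and yoga versus CBT is the difference of its two coefficients.** That contrast can be derived, but the plan does not say it will be. Nor does it say how a logit-scale contrast would be set against a percentage-point margin.

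**The remark about block size need not refer to correlated outcomes.** This is fair, and the point does not depend on it. Section 9.6 gives treatment in groups as its reason for the third level.

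**Conclusion.** The concern holds. The stated .80 has almost no margin for the clustering that the plan itself models. For a cohort-aware test at 95 per arm, power by the normal approximation is 1–2 points below .80 at ICC 0.01, 0.72–0.75 at 0.05 and 0.65–0.71 at 0.10. For a test that ignores cohorts the power loss is smaller, and type I error is clearly inflated only from about ICC 0.05. All of this rests on assumed ICCs, equal response of 57.9% in both arms, and one-sided alpha 0.05 inferred from the printed sample size. This should be fixed, because the plan leaves open the standard error of the test that sizes its two main arms.

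**What to change.** In Sections 9.2 and 9.5, with no added patients:

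1. State an assumed intra-cohort ICC, or a range, with its basis. Restate the power at 95 per arm using 1 + (m − 1) × ICC, for the test that will actually be used.
2. Specify that the confidence interval or test for the yoga minus CBT response difference uses a cohort-aware standard error, consistent with the third level in 9.6.
3. State the alpha and sidedness used for the sizing and for the test. The figure of 95 is consistent with one-sided 0.05.

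A separate minor correction, unrelated to clustering: the margin sentence in both sections prints 56.7 where 57.9 is needed. (57.9 − 22.2)/2 = 17.85, whereas (56.7 − 22.2)/2 = 17.25.

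The cost is protocol and SAP wording and one variance specification. The downside is a less favourable stated power.
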